Date: May 24, 2004

Re: LETTER OF AMENDMENT FOR HPTN 034, Version 1.0 October 15, 2001 HPTN 034 and Substudies 034 A and 034 B

HPTN HIV Incidence and Participant Retention Protocol, Pune, India:

Version 1.0, October 15, 2001

Principle Investigators: [name], JHU, USA

[name], NARI, Pune, India

THE FOLLOWING INFORMATION IMPACTS THE HPTN 034 STUDY AND MUST BE FORWARDED TO YOUR INSTITUTIONAL REVIEW BOARD (IRB)/ETHICS COMMITTEE (EC) AS SOON AS POSSIBLE FOR THEIR INFORMATION AND REVIEW. THIS MUST BE APPROVED BY YOUR IRB/EC BEFORE IMPLEMENTATION.

THE FOLLOWING INFORMATION MAY ALSO IMPACT THE SAMPLE INFORMED CONSENT. YOUR IRB/EC WILL BE RESPONSIBLE FOR DETERMINING THE PROCESS OF INFORMING SUBJECTS OF THE CONTENTS OF THIS LETTER OF AMENDMENT.

PLEASE FILE THIS LETTER AND ANY IRB/EC CORRESPONDENCE IN YOUR REGULATORY FILE AND OTHER PERTINENT FILES. YOU ARE NOT REQUIRED TO SUBMIT THESE DOCUMENTS TO THE PROTOCOL REGISTRATION OFFICE UNLESS THE CHANGES RESULT IN A CHANGE TO THE INFORMED CONSENT FOR YOUR SITE.

Summary of Revisions

Protocol Summary (Page No. 5 of 33):

Population:	Cohort of HIV discordant couples and HIV negative high-risk women will be	
	increased.	
Study Duration	n: Study duration will be extended by 5.5 months.	
Primary Obje	ctives: Cohort of HIV discordant couples and HIV negative high-risk women will be	
	increased.	
Section 1.1	Duration of study will be increased by one year.	
Section 1.1	Duration of upcoming studies will be increased by 6 months.	
Section 1.2.2	Cohort of HIV discordant couples and HIV negative high-risk women will be increased.	
Section 1.3.6	Evaluation of follow up visits will be increased.	

Section 2.3	Cohort of HIV discordant couples and HIV negative high-risk women will be increased.		
Section 3.1	Cohort of HIV discordant couples and HIV negative high-risk women will be increased.		
Section 3.3.3	Duration of the follow-up period will be increased.		
Section 4 (Screenin	Section 4 (Screening / Enrollment)		
	Cohort of HIV discordant couples and HIV negative high-risk women will be increased.		
Section 4.2	Cohort of HIV discordant couples and HIV negative high-risk women will be increased.		
Section 4.3	Duration of the follow-up period will be increased.		
Section 5.2	Cohort of HIV discordant couples and HIV negative high-risk women will be increased.		
Section 5.3.1	Cohort of HIV discordant couples and HIV negative high-risk women will be increased.		
Section 5.3.2	Cohort of HIV discordant couples and HIV negative high-risk women will be increased.		
Section 5.4	Cohort of HIV discordant couples and HIV negative high-risk women will be increased.		
Appendix 1.0	Duration of the follow-up period will be increased.		

The protocol team roster is updated.

Implementation

Once this Letter of Amendment is approved by the Division of Acquired Immunodeficiency Syndrome (DAIDS) (both the medical officer and Regulatory Affairs Branch), it will be submitted to the DAIDS through the Regulatory Compliance Center (RCC) for informational purposes.

If the HPTN 034 protocol is amended in the future, all changes described in this letter of amendment will be incorporated into the next version.

Modifications are indicated by strikethrough or **bolded** text.

Protocol Summary (Page No. 5 of 33):

Population:	400 540 adult HIV uninfected non-sex worker women attending STD clinics and 400530 HIV discordant couples from Pune, India	
Study Duration:	Accrual will require 12 17.5 months and participants will complete one year one and half years of follow up	
Primary Objectives:	To determine the current incidence of HIV among a cohort of 400 540 newly identified high-risk women in Pune as well as among 400 530 HIV uninfected partners of HIV infected persons.	

Section 1.1	Thus the HPTU in Pune is planning for the initiatiation of these 2 clinic -based phase 3 clinical trials over the next two three years.	
Section 1.1	In anticipation of the initiation of the HPTN 035 trial within the next year and HPTN 052 trial within the next $\frac{24}{20}$ months.	
Section 1.2.2	In addition to the overall HIV sero incidence estimates, this protocol will also provide the first HIV incidence estimate for 400 530 HIV uninfected partners of 400 530 HIV infected individuals in India.	
Section 1.3.6	For this analysis, HIV antibody sero negative patients who received test results within 90 days of screening and were enrolled in the follow-up study were evaluated for a return visit for the time periods 91-180 days, and 181 to 360 days, and 361 to 425 days.	
Section 2.3	This protocol will enroll and follow 400 540 women attending STD clinics, who are found at screening to be HIV antibody negative. In addition 400 530 HIV uninfected partners of individuals found HIV infected at screening, will be followed together as HIV discordant couples.	
	As mentioned, we will also attempt to enroll 400 530 HIV discordant couples in a prospective cohort, as part of this 034 protocol.	
	The 400 540 HIV-negative women, as well as the 400 530 HIV-discordant partners will enroll in the study and then complete quarterly follow-up visits over the course of the $\frac{12}{17.5}$ months following enrollment.	
	In addition, if our recruitment goal of 400 530 discordant couples has not been met, these seroconverters will be encouraged to refer their sexual partner for HIV screening.	
Section 3.1	This study will enroll 400 540 adult non-sexworker women attending STD clinics in Pune, India. In addition, 400 530 HIV-discordant couples will be enrolled. Thus, a total of 800 1070 HIV-uninfected and 400 530 HIV-infected participants will be enrolled.	
	Following initial HIV screening, 400 540 HIV-uninfected women and 400 530 HIV- discordant couples (total n=1200 1600) will be offered enrollment in this study based upon the following eligibility criteria.	
Section 3.3.3	Each partner is available for at least $\frac{12}{17.5}$ months of study follow-up.	
	Each couple has stated intention to continue their relationship for the duration of the study $[\frac{12}{17.5}]$ months].	
Section 4	Of the 1600 HIV-uninfected individuals, we will anticipate enrollment of approximately 400 540 new non-sex worker women over the first 12 23 months into this follow-up study of HIV serocoversion.	
	We will also enroll 400 530 HIV-discordant couples.	
Section 4: (Screen	ing / Enrollment)	

 $(n = \frac{1200 \ 1600}{1600} \text{ enrolled}, \frac{400 \ 540}{100} \text{ HIV} - \text{ve women} + \frac{400 \ 530}{100} \text{ HIV} \text{ discordant couples})$

- Section 4.2 Of the 800 1070 HIV-uninfected participants targeted for enrollment, 400 530 will be enrolled with their HIV-infected sexual partners. These 400 530 HIV-discordant couples will be consented, enrolled and followed as couples, using identical data forms...as for the 400 540 HIV-uninfected women in this study.
- Section 4.3 Follow-up visit will occur every 3 months for $\frac{12}{17.5}$ months.
- Section 5.2 As outlined below, we will calculate 6 and 12 month retention rates for the 400 540 newly identified and enrolled HIV uninfected women, as well as the 400 530 HIV discordant couples
- Section 5.3.1 Approximately 2000 new STD patients will be screened over the next year and 400 540 newly identified high-risk women and 400 530 HIV serodiscordant couples attending the STD clinics in Pune will be enrolled in order to estimate the current HIV incidence.

This 034 protocol will enroll 400 540 women, as well as 400 530 HIV-uninfected partners of HIV infected persons and follow them for 1-year one and a half years with an anticipated 90% semiannual retention.

The 400 540 high-risk women participants will accrue an estimated 348 470 person years of follow-up by July 2003 August 2004.

Amongst the discordant couples, the 400 530 HIV-uninfected partners will accrue 348 461 person years of follow-up,

- Section 5.3.2 Amongst the 400 540 HIV-negative women enrolled in the study, we are targeting a 95% annual retention rate. Using that expected rate, the sample size of 400 540 will allow the estimation of the retention rate to within + 2.14% (95%CI). Similarly among the 400 530 HIV uninfected members of sero discordant couples we estimate that we will achieve 95% annual retention.
- Section 5.4 Overall retention rates will be calculated for all 1200 1600 subjects. In addition, the retention rates of the subset of 400 540 women and 400 530 discordant couples will be separately calculated.

Separate estimates of seroincidence will be calculated for the 400 540 women and the 400 530 HIV-uninfected partners.

To determine the current incidence of HIV among a cohort of 400 540 newly identified highrisk, HIV-negative women in Pune.

In addition, a separate estimate of the HIV incidence among 400 530 HIV-uninfected partners of HIV-infected subjects will also be estimated separately.

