Division of AIDS (DAIDS) US National Institute of Allergy and Infectious Diseases (NIAID) US National Institutes of Health (NIH)

I, the Principal Investigator, agree to conduct this study in full accordance with the provisions of this protocol. I agree to maintain all study documentation for a minimum of five years from the end of the study, unless directed otherwise by the HPTN CORE. Publication of the results of this study will be governed by HPTN and DAIDS policies. Any presentation, abstract, or manuscript will be made available by the investigators to the HPTN Manuscript Review Committee and DAIDS for review prior to submission.

I have read and understand the information in this protocol and will ensure that all associates, colleagues, and employees assisting in the conduct of the study are informed about the obligations incurred by their contribution to the study.

Name of Principal Investigator

Signature of Principal Investigator

Date

HPTN Protocol 034 HPTN HIV Incidence and Participant Retention Protocol, Pune, India PROTOCOL SUMMARY

Design: This protocol is a cohort study of HIV incidence in patients attending STD clinics in Pune, who will be eligible for screening and participation in 2 upcoming HPTN clinical trials of vaginal microbicides (HPTN 035) and antiretroviral drugs (HPTN 052).

Population:	400 adult HIV-uninfected non-sex, worker women attending STD clinics and 400 HIV discordant sexual couples from Pune, India.
Study Duration:	Accrual will require 12 months and participants will complete one year of follow-up. Therefore, the entire study should be completed within approximately 24 months.

Primary Objectives:

- 1. To determine the current incidence of HIV among a cohort of 400 newly identified high-risk, women in Pune, as well as among 400 HIV-uninfected partners of HIV-infected persons.
- 2. To determine the retention rate in high-risk women, as well as HIV discordant couples, among a target population eligible for screening for upcoming HPTN 035 and 052 trials.

Primary Endpoints:

- Current HIV seroconversion rates in HIV-uninfected participants.
- Retention rates in high-risk women, as well as discordant couples.

Secondary Objectives:

- 1. To assess risk factors for HIV and other STDs.
- 2. To identify and address potential barriers to participation and high-level retention (>95% 1 year retention) for the upcoming HPTN clinical trials.

Secondary Endpoints:

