Our previous experience with enrollment and follow-up for clinical trials suggests that this 81% retention rate will be increased and sustained with effective community education about the specific risks, benefits and objectives of participating in HPTN clinical trials. However, this HPTN protocol will target a goal of at least 90-95% 1 year retention in our observational cohort for newly identified and enrolled high-risk individuals, in anticipation of the need for this level of retention for the upcoming HPTN trials. With a current follow-up rate of >80% for our observational study of HIV transmission and follow-up rates of >90% for our other prospective clinical studies, including three HIV clinical trials, we are confident that this protocol will help us identify the procedures required to achieve the excellent retention of participants required for the HPTN 035 and 052 trials.

One of the proposed HPTN trials for Pune (HPTN 052) will enroll HIV discordant couples. The Pune site has some experience through the HIVNET 023 couples study with screening, enrollment and follow up of discordant couples. However, this 034 protocol specifically includes efforts to identify and enroll up to 400 HIV discordant couples in an observational cohort study. This will provide essential experience and a preliminary base for the enrollment of discordant couples into future HPTN clinical trials. NARI has a HIV Reference Clinic facility on the premises of National Institute of Virology, Pune. This site is proposed for recruiting HIV discordant couples in various clinical trials. In addition, we have also successfully negotiated a clinic space in Talera Hospital in Chinchwad, an adjoining Municipal hospital and we have initiated an HIV reference clinic in this center that will also serve as a referral source for HIV discordant couples. In addition, through community outreach to local physicians, hospitals and clinics, NARI has become a regional reference center for the care of HIV infected individuals. We anticipate that this referral base will also provide additional opportunities to identify HIV-infected index partners for enrollment of discordant couples.

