2.2 Secondary Objectives

- To determine risk factors for HIV transmission in high-risk women and among HIV discordant couples.
- To identify and address potential barriers to participation and high-level retention (>95% 1 year retention) for the upcoming HPTN clinical trials.

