3.5 Withdrawal

Once a participant has enrolled in the cohort study, we will make every reasonable effort to retain him/her for at least 12 months of follow-up. Retention rates of at least 95% are targeted for this observational cohort study. However, participants will have a right to withdraw from the study for any reason at any time if they so desire. The investigator also may withdraw participants from the study in order to protect their safety and/or if they are unwilling or unable to comply with required study procedures. Participants also may be withdrawn if the sponsor or regulatory authorities terminate the study prior to its planned end date.

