5.3.2 Study Retention Rates

Amongst the 400 HIV-negative women enrolled in the study, we are targeting a 95% annual retention rate. Using that expected rate, the sample size of 400 will allow the estimation of the retention rate to within $\pm 2.14\%$ (95% CI). If the estimated retention were to drop to 90% the associated 95% CI is $\pm 3.0\%$, and if it were to drop as low as 80%, the sample size would allow the calculation of a 95% CI of $\pm 3.9\%$. Similarly, amongst the 400 HIV-uninfected members of serodiscordant couples we estimate that we will achieve 95% annual retention. This number of couples will allow for a 95% confidence interval of $\pm 2.14\%$, and for 90% retention the interval increases to $\pm 3.0\%$.

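### Retention of discordant couples is a primary endpoint, but its expected rate is stated for uninfected partners, its calculation counts individuals, and the stated precision does not fit 530 couples

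*Supplement*

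**What the plan says.** The Protocol Summary lists as a primary endpoint "Retention rates in high-risk women, as well as discordant couples". The matching primary objective is in Section 2.1.

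Section 5.3.2, as amended, gives the expected rate for one member of each couple: "Similarly among the 400 530 HIV uninfected members of sero discordant couples we estimate that we will achieve 95% annual retention". The next sentence of the Version 1.0 text moves to the couple as the unit: "This number of couples will allow for a 95% confidence interval of" ±2.14%, widening to ±3.0% at 90% retention. The amendment changes 400 to 530 in the first of these sentences and gives no new precision for the couples cohort. For the women it leaves ±2.14% beside the new n of 540.

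Section 5.4 promises that "the retention rates of the subset of 400 540 women and 400 530 discordant couples will be separately calculated". Its rule, unchanged from Version 1.0, takes enrolled participants as the denominator. The numerator is participants who complete a follow-up pre-test visit in the interval, or who are already known to be infected or to have died. Sections 2.3 and 4.2 say that HIV-infected partners are not retested.

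On the goal, Section 3.5 says "Retention rates of at least 95% are targeted for this observational cohort study", and Sections 5.3.1 and 5.3.2 also give 95% annual retention. Section 1.3.6 says "this HPTN protocol will target a goal of at least 90-95% 1 year retention".

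**The concern.** Three quantities could be reported as couple retention: the rate among 530 uninfected partners, the rate among the 1,060 individuals in the subset, or the proportion of 530 couples with both members retained. The endpoint's wording points to the last, the planning assumption to the first, and the participant-based rule of Section 5.4 to the second. They agree only if partners are always kept or lost together.

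Section 1.2.3 says the site needs to learn whether it can enroll and retain discordant couples for HPTN 052. A person-level figure answers a more favourable question. Under Section 4.9, interim results on the primary endpoints also inform whether activities end and resources move to the trials, so the figure has a practical use.

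**Working it through.** **Inputs from the documents.** Expected retention 95% per year for the uninfected partner (Section 5.3.2). n=400 in Version 1.0 and n=530 after the amendment. Stated precision ±2.14 points at 95% and ±3.0 at 90%.

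**Assumptions not in the documents.** The index partner is also retained at 95%. The within-couple correlation of retention, ρ, is unknown and is shown over a range.

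**Step 1: reproduce the plan's figure.** Half-width = 1.96 × √(p(1−p)/n).
- n=400, p=0.95: 1.96 × √(0.0475/400) = 2.14 points, as stated.
- n=400, p=0.90: 1.96 × √(0.09/400) = 2.94 points, stated as 3.0.

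**Step 2: same formula at the amended size, uninfected partner as unit.**
- n=530, p=0.95: 1.96 × √(0.0475/530) = 1.86 points.
- n=530, p=0.90: 1.96 × √(0.09/530) = 2.55 points.
- For the women, n=540, p=0.95: 1.84 points.

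The ±2.14 is thus the n=400 value carried forward.

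**Step 3: couple as unit, both members retained.** P(both) = p² + ρ·p(1−p), with p=0.95, so P(both) = 0.9025 + 0.0475ρ.

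| ρ | Couples with both retained | 95% half-width, n=530 |
|---|---|---|
| 0 (independent losses) | 90.25% | ±2.53 |
| 0.5 | 92.6% | ±2.23 |
| 1 (fully shared loss) | 95.0% | ±1.86 |

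The floor, if the two partners' losses never coincide, is 2 × 0.95 − 1 = 90%. Conversely, under independence, 95% of couples with both retained needs √0.95 = 97.5% per partner.

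**Step 4: the goal.** Take 490 of 530 couples retained: 92.5%, exact 95% interval 89.9% to 94.6%. This meets the goal in Section 1.3.6 read at its lower end and falls short of the 95% in Sections 3.5, 5.3.1 and 5.3.2. Outside 90% to 95% the two wordings lead to the same reading.

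**The case against.** The strongest reply is that retention is only estimated and tabulated, and every component can be recovered from the data. Much of this stands, and it limits the point in several ways.

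- A reader might infer that the study could be declared a success or failure at will. The documents contain no test, threshold rule or pass/fail criterion for retention, so that does not follow.
- A reader might count three competing targets by adding the "high-level retention (>95% 1 year retention" wording of Section 2.2. That objective concerns barriers to retention for the upcoming trials, and Section 1.2.3 likewise describes what a trial will need. For 530 couples, above 95% and at least 95% are in any case the same criterion: 503 (94.9%) fails both and 504 (95.1%) passes both. The 90% semiannual figure in Section 5.3.1 is a sample-size assumption, not a goal.
- A reader might say the couples cohort was sized on the wrong unit. Section 5.3.1 derives its size from HIV incidence; Section 5.3.2 only states the retention precision that follows.
- Section 5.3.2 already gives ±3.0 at 90%, which is wider than any couple-level half-width above. The plan does not promise too little uncertainty at that rate.
- Couples enroll together, intend to stay together and are followed as couples (Sections 3.3.3 and 4.2). Shared loss is likely, so the independent case is one end of the range and not the expectation.

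It might also be said that no passage plans to present the uninfected-partner rate as the couple rate. That is true. But a person-level rate is what the Section 5.4 rule yields, and choosing a couple-level reading would require a rule that is absent.

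**Conclusion.** The point holds as a mismatch of unit in a primary endpoint. Following Section 5.4 as written gives a person-level rate for an endpoint framed on couples. At 95% per partner, the proportion of couples with both members retained is between 90% and 95%, so the possible overstatement runs from zero to 5 points. Where it falls depends on how far partners are lost together and on the index partner's retention, neither of which the documents give.

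The precision is out of date: ±2.14 fits neither the uninfected partners (±1.86) nor, except by coincidence, the couples (about ±1.9 to ±2.5). For the partners and for the 540 women the stated figure errs on the wide side. The conflict over the goal is narrower: it is between the background text and the 95% used elsewhere for this study, and it matters only for a rate between 90% and 95%.

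**What to change.** - **Section 5.4:** calculate couple retention as the proportion of enrolled couples with both members retained at 12 months, and report uninfected-partner and index-partner retention beside it. Say what counts as a completed visit for the index partner, who is not retested, and how the existing allowance for infection or death applies to a couple.
- **Section 5.3.2:** name the unit and restate the precision for n=530. At 95% this is ±1.86 points and at 90% ±2.55. Update the women's figure to ±1.84 at n=540.
- **Section 1.3.6:** align the goal with the 95% of the statistical section.

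The cost is protocol wording and one more tabulation from data already collected. No extra participants or visits are needed. The drawback is a less favourable expected figure for couples than for individuals.

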CLARIFICATION MEMO # 2

HPTN 034, VERSION 1.0:

HIV Prevention Preparedness Study

March 7, 2003

Summary of revision

Sera of HPTN 034 study participants will be initially screened with ELISA kits either commercially available or supplied by National AIDS Control Organization (NACO), India. Sera that are positive will be confirmed by re-testing with commercially available or NACO supplied kits.

Rationale

The HPTN 034 study was initiated at Pune site on 16th September 2002. The current protocol specifies that certain brands of HIV ELISA kits be used for initial testing and confirmation. However, it is practically difficult to use these specific kits due to inconsistent availability in the market. NARI has been using commercially available or NACO-supplied kits for the last 9 years with satisfactory results. The NARI CORE laboratory has certified all HIV ELISA test kits via an internal quality control procedure, whether commercially available or NACO-provided. Hence, we would like to propose a change in the protocol text allowing for any brand of ELISA kit to be used for the study.

Implementation

The following modification will be made to Protocol HPTN 034 (Version 1.0 dated October 15, 2001) to implement the revisions described above. This modification will be incorporated into the body of the protocol in the next version.

Section 4. Study Procedures, 4.4 Detection of HIV infection, paragraph 1, Lines 2-5 (page 20 of 33)

Original Text:

"Sera will be initially screened with the Genetic Systems combination ELISA kit for detection of HIV-1 and HIV-2, which is our current ELISA screening method. Specimens that are positive by Genetic Systems ELISA will be confirmed for HIV-1 or HIV-2 infection by re-testing with a different ELISA (UBI HIV 1/2 EIA, United Biomedical, USA)."

New Text:

"Sera of HPTN 034 study participants will be initially screened with ELISA kits either commercially available or supplied by National AIDS Control Organization (NACO), India. Sera that are positive will be confirmed by re-testing with commercially available or NACO supplied kits."

HIV Prevention Trials Network

CLARIFICATION #1

HPTN 034, version 1.0:

HIV Prevention Preparedness Study

December 27, 2002

Summary of Revisions

- 1. Screened volunteers will be called for HIV test results and post-test counseling 7-14 days after their screening visit. The volunteers having HIV negative serology within 22 days will be enrolled.
- 2. Follow up visit will occur every 3 months for one year. The participants coming within 22 days of their scheduled follow up visit will be taken for follow up.

Rationale

The current protocol specifies the time frame of 7-14 days for HIV test result visit. However it does not specify the time period after which the screened participant become ineligible and should be rescreened. The protocol also does not specify variation of time period that can occur for the scheduled follow up visit.

Implementation

The following modifications are made to Protocol HPTN 034 (version 1.0, dated October 15,2001) to implement the revisions described above. These modifications will be incorporated into the body of the protocol in the next version.

1. Section 2.3 Study design, page 13, paragraph 1

The passage ' scheduled to receive their HIV tests and post test counseling at a study enrollment visit 7-14 days later.' Will be changed to 'scheduled to receive their HIV tests and post test counseling at return for test result visit 7-14 days later.' The additional sentence which is to be added as the last line of the same paragraph reads as ' Regardless of the number of screening visits required

enrollment of HIV negative participant must be completed within 22 days from the time of first screening tests and exams.'

2. Section 4.2 Enrollment, page 19, paragraph 2

The passage 'who will answer all questions posed by patients' will be changed to 'who will answer all questions posed by patients provided the HIV seronegative participants return to the study clinic within 22 days of their screening visit.

- 3. Section 4.3 Follow-up visits, page 19, paragraph 3
- 3. The following sentence will be added after the passage 'The follow up visit will occur every three months for one year' which reads as 'The follow up visit will occur every three months for one year. The participants coming within 22 days of their scheduled follow up visit will be taken for follow up otherwise they will be rescreened.

HPTN HIV Incidence and Participant Retention Protocol Pune, India

HPTN Protocol 034 A Study of the HIV Prevention Trials Network

Sponsored by:

Division of AIDS US National Institute of Allergy and Infectious Diseases US National Institutes of Health

Protocol Chair(s):

[name] [name] [name]. MPH

> Final Version 1.0 15 October 2001

HPTN Protocol 034 HPTN HIV Incidence and Participant Retention Protocol Pune, India

TABLE OF CONTENTS

		TEAM ROSTER	
		FOR SIGNATURE PAGE	
